Title: The Effect of Binasal Occlusion on Balance Following a Concussion: a Randomized Controlled Trial Protocol

NCT number: not available

Document Date: November 16, 2017

THE EFFECT OF BINASAL OCCLUSION ON BALANCE FOLLOWING A CONCUSSION: A RANDOMIZED CONTROLLED TRIAL PROTOCOL

ABSTRACT

Introduction

While most individuals will recover within the first month after concussion, a significant number will continue to experience dizziness, balance problems, cognitive deficits, and vision problems. Single-task measures of static balance may not be sensitive enough to capture mild postural changes still associated with incomplete recovery. Increasingly there is an interest in dual-task paradigms of balance assessment as a more accurate representation of functional postural control associated with activities of daily living and sport participation. Binasal occlusion (BNO) has been proposed as a means of providing visual stabilization to improve postural control in individuals with vision-related balance problems following a concussion. The purpose of this study is to assess the efficacy of BNO during the performance of both single and dual-task conditions in adults who continue to experience dizziness one month or longer following a concussion. It is hypothesized that BNO will improve balance and saccadic eye function, and reduce symptoms. This article presents the research protocol for this study.

Methods and analysis

This study is a randomized crossover design balanced with respect to first-order effects. Participants will be recruited and randomly assigned to one of two treatment sequences, binasal occlusion (BNO) or non-occluded vision. Both groups will perform the same static balance tasks, including quiet stance performed during target-focused vision and a visually based cognitive dual-task. Following a short washout period, participants will repeat the balance tasks under the alternate treatment condition. The primary outcome measure is centre of pressure (COP) velocity in both the medial-lateral (M/L) and anterior-posterior (A/P) planes and 95% ellipse. Secondary outcome measures include saccadic eye function and self-report measures of symptoms and disability (neck and dizziness related). **Ethics and dissemination:**

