Studies have compared single- with dual-task performance on COP post-concussion, (Degani et al., 2017) or the presence of saccadic dysfunction post-concussion, using visually-based cognitive dual-tasks (Rizzo et al., 2016; Subotic et al., 2017). However, to date, no study has directly compared the effect BNO as an intervention on measures of COP velocity, objective metrics of saccadic eye movement, and symptoms during the performance of single- and visually-based cognitive dual-task balance conditions in a concussion population. This makes it difficult for clinicians to make evidence-informed choices in the management of individuals who experience persistent balance deficits beyond the expected period of normal recovery following a concussion. This study aims to address this gap by assessing the efficacy of a BNO intervention trial in adults with persistent post-concussion balance problems compared with a control condition using both single and visually-based cognitive dual-task balance paradigms. The study is designed as a randomized controlled crossover test with a sample size calculated a priori to ensure the contribution of high quality evidence to a nascent body of literature.

OBJECTIVES

Purpose

The overarching research question is the following: What is the effect of BNO compared with no binasal occlusion on measures of static balance, saccadic eye movement functions, and symptoms in adults who continue to experience dizziness one month or longer following a concussion? The specific objectives of this study are (1) to measure the effect of BNO on postural sway, compared with non-occluded vision during quiet stance on a force plate; (2) to examine the impact of BNO on postural sway while performing a visually based cognitive dual-task compared with target-focused vision, as measured during quiet stance on a force plate; (3) to compare the effect of BNO on saccadic eye function, compared with non-occluded vision during a timed reading task. Saccadic eye function will be quantified as time to completion during the KDT and the total number of saccades; (4) to determine the relationship between a rapid number naming task and observable saccadic eye function; (5) measure the association between self-reported symptoms, disability, and objective measures of balance in adults who continue to experience dizziness longer than one month after concussion.

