It is hypothesized that BNO will improve postural sway during a visually based cognitive dual-task more than during quiet stance. We also hypothesize that time to completion of a timed reading task will correlate positively with saccadic eye function, and that both will show improvement with BNO. It is further hypothesized that perceived disability due to dizziness and neck pain would be greater in

individuals with increased postural sway. This article presents the research protocol for this study.

METHODS

Design

This cross-sectional study will examine the effect of BNO on balance in adults aged 18-65 years who continue to experience symptoms one month or more following a concussion. A 2-task, 2-period, 2 treatment condition randomized crossover study design will be used in order to be balanced with respect to first-order effects, as each condition will precede the other condition only once. Potential participants will be screened for eligibility during a telephone interview. Following enrollment, they will be randomized to one of two condition sequences and act as their own control group. Participants will perform two different balance tasks repeated under both treatment (BNO) and control (no BNO) conditions. The treatment/control conditions will be the same for each participant with only the order of each treatment/control sequence randomized. Post-concussion syndrome is considered chronic and stable, and thus suitable for a crossover study design. Likewise, the application of BNO is intended to improve immediate functional balance and saccadic eye movement, rather than cure the concussion. No evidence of the effect time of BNO has been reported in the literature. Based on clinical experience of two of the authors, the treatment effect is limited to the time of application, so there should be no carryover effect between conditions and a negligible washout period between trials is considered sufficient. To minimize any risk of potential carryover effects, patients will also be asked to wait the greater of 1 minute, or until all symptoms return to their pre-test baseline before performing the subsequent task. A summary of the study design is available in Figure 1. All study procedures will be conducted at one of two private rehabilitation clinics in Ottawa, Canada.

Participants

Patient selection

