During a telephone screening interview, potential participants will speak with a member of the research team to confirm study eligibility, to review details of the study protocol, and to enroll in the study if deemed suitable. During this discussion, potential participants will be given the opportunity to request an electronic copy of the informed consent form to review prior to meeting with the study team. Once enrolled, participants will attend an in-person testing session at one of the two trial locations. At this session, the research team will review: (1) the purpose of the study; (2) how the randomization process works; (3) a general overview of the testing conditions, and the self-report outcome measures. A thorough discussion of potential risks and benefits associated with participation in the study will then take place, as well as the assurance that participants may withdraw from the study or request a rest at any time during the study without consequence or without effect on the medical care that they receive. Each participant will be given a hard copy of

the informed consent form for signature and an extra copy to take home. Participants will be given as much time as required to re-read and complete the informed consent form, as well as the opportunity to ask for and receive clarification for questions as necessary.

Sample size

40 participants will be recruited for the present study. A power analysis based on COP excursion using a force plate with adults following a concussion has been calculated to determine the number of participants that need to be recruited for the present study. A change in COP excursion by more than 5cm will be considered to be significant, as this represents the minimal detectable change with a 90% confidence interval (Goble, Manyak, Abdenour, Rauh, & Bawega, 2016). A two-tailed analysis will be made with alpha level set at 0.05 and power set at 80%. Due to the nature of this crossover design, loss to follow-up is not expected, and therefore not accounted for in the sample size determination.

Randomization

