Participants will be randomly assigned to one of two groups for a crossover study design. Each group will complete both arms of the study, randomized to sequence, starting with either the control condition or the intervention condition. The intervention condition consists of performing the identical balance tasks while wearing glasses overlaid with BNO. Researchers performing the intervention will not be blinded to group allocation due to the crossover design.

OUTCOME MEASURES

For each arm of the study, participants will complete two trials of static balance while standing on a force plate that will record movement of the center of pressure (COP) under their feet. Sensors from an electromagnetic tracking system will also be attached to each participant at the base of the skull, T5, and L5 along the spine, collecting acceleration of movements, angular velocity of movements, and angular rotation of the earth. The sensors will record accelerations of movements, angular velocities, and angular rotations. Throughout each trial condition, Tobii™ eye tracker glasses will be worn to measure and record saccadic eye movements and time to task completion.

Primary outcome

Balance – COP

Measurement of postural sway as an indicator of persistent balance impairment post-concussion builds upon previous studies demonstrating increased postural sway in the acute period following a concussion (Goble et al., 2016). The primary outcome of interest is the mean M/L and A/P velocity of COP, in addition to the 95% ellipse during different conditions of static balance. The minimal clinical difference

considered to demonstrate a change in postural sway is 5cm based on a previous validation study in a concussed population (Goble et al., 2016).

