For balance task B, participants will be asked to stand shoulder width apart on the BTS with their hands on their hips. Participants will be asked to complete a cognitive task while they maintain their balance. The visually based cognitive dual-task will involve the participants performing the King-Devick Test (KDT). Test cards will be fixed to a wall and positioned 12 inches from the participant's face at eye level. Participants will be asked to read the numbers out loud as quickly and as accurately as possible, from left to right, beginning at the top left corner of each test card. The total time to read all 3 test cards and the total number of errors committed will be recorded. If a participant makes an error, they will be asked to restart the test. The test usually takes less than two minutes to complete. Participants who complete the KDT in less than 2 minutes will be asked to restart the test from the beginning and continue reading for the remainder of the test period. Those individuals who require more than the allotted 2 minutes to complete the KDT will continue with the rapid number naming task until completion, and COP data will stop being collected at 2 min.

Throughout each trial, participants will be fitted with a pair of Tobii™ eye tracking glasses that will record their eye movements.

Control condition: normal vision

During the control arm of the trials, the eye tracking glasses will remain unobstructed and vision will not be occluded.

Experimental intervention: BNO

During the intervention arm of the trials, strips of occlusive material will be placed on the medial portion of each lens of the Tobii[™] eye tracking glasses to occlude central integrated vision.

Planned statistical analyses

Baseline characteristics for participants will be compared with descriptive statistics (mean, SD, n, %).

The primary objective, the effect of BNO on postural sway, will be addressed by using a dependent t-test to compare differences between treatment conditions for each COP variable. A similar analysis using a dependent t-test (group^xKDT_{time to} completion) will be performed to assess the secondary objective, the effect of BNO on reading. Additionally, a Wilcoxon Signed Rank test will be used to determine if there is a significant difference in the number of saccades completed on the KDT between

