the control and intervention conditions. Finally, correlations among self-report measures of disability (DHI and NDI) and symptoms (PCSS), and the 3 dependent measures will be calculated using Spearman's rho for non-parametric data.

Ethics and Dissemination

The possibility of fatigue, an increase in post-concussion symptoms, and problems with balance while completing the trials of balance will be disclosed to potential participants. Participating in this study is very low risk and does not constitute more as compared with usual care that a patient would receive. Participants will be required to provide informed consent, and may withdraw from the study at any time without explanation.

Results from this study will be shared with healthcare professionals and academics at professional conferences and through manuscripts to peer-reviewed journals. Publication topics include the efficacy of BNO on postural sway and saccadic eye function; the impact of a cognitive dual-task on balance; the relationship between KDT time and observable saccadic eye function; and the association between selfreported measures of symptoms, disability, and objective measures of balance.

Conclusion: Impact on clinical practice

The assessment and treatment of vision related issues has been identified as an integral part of the rehabilitation of patients who have suffered a concussion. The efficacy of BNO as a treatment modality in the management of individuals with post-concussion syndrome is currently poorly understood. This article describes the protocol for a randomized controlled trial that tests the efficacy of BNO on static balance for adults with persistent dizziness and balance problems one month or more after concussion. Results from primary and secondary outcome measures will contribute to our understanding of the efficacy of BNO in relation to postural sway, saccadic eye function, symptoms, and disability. This study will begin to fill in the gaps with respect to evidence-based vision therapy to manage persistent dizziness post-concussion.

Current Study Status

This trial is set to begin recruitment in November 2017.

Broglio, S. P., Tomporowski, P. D., & Ferrara, M. S. (2005). Balance performance with a cognitive task: A dual-task testing paradigm. *Medicine and Science in Sports and Exercise*, *37*(4), 689–695.

https://doi.org/10.1249/01.MSS.0000159019.14919.09

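### The hypothesis that BNO improves sway more in the dual task than in quiet stance has no matching test: the stated paired t-test compares conditions, not the BNO effect between tasks

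*Protocol*

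**What the plan says.** **Hypothesis (Protocol, Objectives, Purpose).** "It is hypothesized that BNO will improve postural sway during a visually based cognitive dual-task more than during quiet stance". It is the first hypothesis listed in that section.

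**Objectives 1 and 2 (same section).** Objective 1 is "to measure the effect of BNO on postural sway, compared with non-occluded vision during quiet stance on a force plate". Objective 2 is "to examine the impact of BNO on postural sway while performing a visually based cognitive dual-task compared with target-focused vision", again during quiet stance on the force plate.

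**Abstract.** A broader hypothesis that does not compare tasks: "It is hypothesized that BNO will improve balance and saccadic eye function, and reduce symptoms".

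**Design and Balance Testing Protocol.** Each participant performs task A (quiet stance, eyes on a dot) and task B (standing while doing the King-Devick Test, KDT) under both BNO and control. Only the order of the two conditions is randomized.

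**Planned statistical analyses.** "The primary objective, the effect of BNO on postural sway, will be addressed by using a dependent t-test to compare differences between treatment conditions". One such test is planned per COP variable. The section does not say whether this is done per task or over both tasks. The other analyses are a paired t-test on KDT time, a Wilcoxon signed rank test on saccade counts, and Spearman correlations of the self-report scores with three dependent measures.

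**The concern.** A hypothesis of the form *larger effect in B than in A* needs a test of the difference between the two effects. The analysis section assigns a named test to sway, but task does not enter into it.

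At stake is the comparative claim only. Followed as written, the trial could report a BNO effect in each task, or one overall, and would still have no stated test or rule for deciding whether the dual-task effect is the larger. The contrast and its scale would then be open to choice after the results are seen.

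**Working it through.** **1. Stated test against stated hypothesis.** Let δA and δB be the mean BNO-minus-control differences in sway in tasks A and B.

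| Question | Null hypothesis | Provided by the stated analyses? |
|---|---|---|
| BNO effect in quiet stance | δA = 0 | Yes, if the t-test is run per task |
| BNO effect in the dual task | δB = 0 | Yes, if the t-test is run per task |
| BNO effect over both tasks | (δA + δB)/2 = 0 | Yes, if the t-test is pooled |
| BNO effect larger in the dual task | δB − δA = 0 | No |

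The pooled version cannot separate the cases of interest. Take the protocol's 5 cm as an example. With δA = δB = −5, the average is −5. With δA = 0 and δB = −10, the average is (0 − 10)/2 = −5 again. The first case contradicts the hypothesis and the second supports it.

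The KDT and saccade tests do not concern sway, and the correlations contain no contrast of BNO or of task.

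**2. Are the data there?** Yes. Each participant gives four cells, so D = (BNO − control in B) − (BNO − control in A) can be computed for everyone.

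**3. The plan's own sample size.** Stated inputs (Sample size): N = 40, two-sided alpha 0.05, power 80%, change of 5 cm in COP excursion. No SD is given, so N = 40 can be neither reproduced nor refuted. Solving backwards for a paired t-test (noncentral t, 39 df), 80% power needs a standardized difference of 0.454, which implies an SD of differences of 5/0.454 = 11.0 cm. The protocol also describes the 5 cm with the words "as this represents the minimal detectable change with a 90% confidence interval". On that reading the SD of differences would be 5/1.645 = 3.04 cm. The two readings differ by a factor of 11.0/3.04 = 3.6.

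**4. Illustrative power for the contrast.** Assumptions, not protocol figures: equal SD of differences in both tasks, and correlation r between the two BNO effects. Then SD(D) = SD × √(2(1 − r)), tested with a one-sample t-test at N = 40.

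| r | SD(D), if SD = 11.0 cm | Power, contrast 5 cm | Power, contrast 2.5 cm |
|---|---|---|---|
| 0 | 15.6 cm | 51% | 17% |
| 0.25 | 13.5 cm | 63% | 21% |
| 0.5 | 11.0 cm | 80% | 29% |
| 0.7 | 8.5 cm | 95% | 44% |

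With SD = 3.04 cm, power is about 100% for 5 cm and 95% or more for 2.5 cm over the same range of r. Power thus runs from 17% to nearly 100% depending on unstated inputs.

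All of this is on excursion, the variable used for the sample size. The Primary outcome section names others: "The primary outcome of interest is the mean M/L and A/P velocity of COP, in addition to the 95% ellipse". For velocity and ellipse, nothing can be computed.

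**The case against.** **A separate SAP may hold the test.** It may, and detail left to a SAP is no fault. But this protocol has its own analysis section that fixes a test for sway, and that test cannot answer the first hypothesis in its Objectives section. The objection limits how serious the point is; it does not remove it.

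**Objective 2.** A reader might infer that objective 2 asks for the same contrast, so that a whole objective is lost. The text does not establish this. Objective 2 has no *more than*. It may intend the contrast, since target-focused vision is task A, or it may mean only the BNO effect within the dual task. The point therefore rests on the hypothesis alone.

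**The mechanism.** The Introduction says that support for the attention mechanism would be better balance under dual-task conditions. That is a within-task effect, which the t-test supplies if run per task. This stands: much of the scientific question survives, but not the comparative claim.

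**Comparing significance across tasks.** A reader might infer that the protocol intends to claim *more than* when the dual task is significant and quiet stance is not. It does not prescribe this, and per-task t-tests also give mean differences with their precision. The size of that error is a reason to state the contrast, not an error in the plan. With equal true effects of 0.2 to 0.454 SD and r from 0 to 0.7, simulation gives dual-task-only significance in about 9 to 25% of trials. It occurs in only 2 to 4% at 0 and at 0.6 SD. The direct test wrongly favours the dual task in about 2.5%.

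**Publication topics.** One listed topic is "the impact of a cognitive dual-task on balance". That is a reporting intention, not a hypothesis, and does not widen the point.

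**Conclusion.** The point holds in a limited form. One stated hypothesis, that the BNO effect on sway is larger in the dual task than in quiet stance, has no test among the stated analyses. This follows from the wording of the hypothesis and of the t-test and depends on no numerical assumption.

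The BNO-versus-control comparison for the primary objective is unaffected, as is the balance part of the abstract's broader hypothesis. It would be wrong to infer that the trial is underpowered for the contrast. Without an SD and a between-task correlation, power cannot be derived, and the figures above only show how wide the range is. The point is worth settling before analysis, because the correction is nearly free.

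**What to change.** Under Planned statistical analyses, state that the existing t-test is run separately for each task, and add:

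> For each COP variable, the hypothesis that BNO improves sway more in the dual task than in quiet stance will be examined as a secondary analysis. A one-sample t-test, with 95% CI, will be applied to the within-participant difference (BNO − control in task B) − (BNO − control in task A), on the absolute scale. The BNO effect within each task will be reported alongside.

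The scale should be named because equal absolute effects are not equal proportional effects when sway levels differ between tasks. A log-scale sensitivity analysis is optional.

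Alternatively, reword the hypothesis as BNO against non-occluded vision within each task and drop the comparative claim.

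In either case, reword objective 2 to say which comparison is meant.

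**Cost.** The first option needs no new data, visits or participants. It adds three secondary tests, one per COP variable, of uncertain power, so a null result should be read from its confidence interval. The second option costs only the *more than* claim.

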Postural stability will be assessed using the BTrackS (BTS) Balance Plate and Explore Balance software (BTrackS, Balance Tracking Systems Inc., San Diego, CA, USA) that is easily portable. The BTS Balance Plate is an FDA registered Class 1 Medical Device designed to measure static balance by calculating the centre of pressure (COP) excursion and velocity of an individual during quiet stance(Goble et al., 2016). Centre of pressure is a proxy measure for postural sway, which is a common measure of balance impairment following concussion (Chang, Levy, Seay, & Goble, 2014; Goble et al., 2016; Kleffelgaard, Roe, Soberg, & Bergland, 2012; Rochefort et al., 2017). Decreased COP displacement can be used as an indicator of recovery or improved postural strategies used to maintain balance after a concussion. The BTS Balance Plate calculates COP using four-sensor technology within a lightweight (<7kg), 0.4m by 0.6 m rectangular platform that is highly accurate and reliable compared with a laboratory-grade force plate (O'Connor et al., 2016).

The Explore Balance software is an application-based program that will be customized to the current study protocol. All balance testing will be performed by members of the research team trained in BTS technology.

Secondary outcomes

Prior to postural sway data collection, participants will be asked to complete 4 questionnaires, including a participant demographic questionnaire, the post-concussion symptom scale (PCSS), the dizziness handicap inventory (DHI), and the neck disability index (NDI).

Baseline Patient Characteristics

Baseline patient characteristics will be collected on pre-prepared data collection forms, and will include age, gender, height, weight, race, marital status, level of education, employment status, mechanism of concussion, and previous history of concussion.

The Post-Concussion Symptom Scale (PCSS)

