The use of symptom scales plays an important role in the diagnosis of concussion and in monitoring recovery. International consensus statements (McCrory et al., 2017), position papers (McCrea, Nelson, & Guskiewicz, 2017), and clinical guidelines (Marshall et al., 2015) recommend symptoms as part of a multimodal assessment that includes measures of neurocognitive status, balance, and cranial nerve function. Clinical best-practice standards recommending the complete resolution of symptoms prior to medical clearance for return to sport highlight the importance symptom evaluation in the management of concussion.

The PCSS is a standardized and easily administered 22-item self-report symptom scale that measures the severity of each symptom experienced that day (Lovell et al., 2006). Symptoms are reported on a 7-point Likert scale, with 0 and 6 representing

anchoring points from the absence of symptoms to the presence of severe symptoms. Results are conveyed as the total symptom score and range from 0-132, with a higher score associated with a higher level of symptoms. Total scores demonstrate high internal consistency in a concussion population (α =0.93), with a 6.8 point change (CI₈₀) associated with a clinical change in symptoms (Lovell et al., 2006).

The Dizziness Handicap Inventory (DHI)

Dizziness is commonly reported post-concussion (Rochefort et al., 2017), and associated with prolonged recovery (Lau et al., 2011). The presence of dizziness has the ability to significantly impact an individual's quality of life by limiting an individual's activities and raising their anxiety. Developed as a standardized measure to evaluate the self-perceived impact of dizziness on everyday life (Jacobson & Newman, 1990), the DHI is a self-report scale that represents the functional, physical, and emotional domains. Internal consistency is high for total scores ($\alpha = 0.89$) and satisfactory for the three subscales ($\alpha = 0.72$ to 0.85). The presence of dizziness-related disability is scored as no (0), sometimes (2), or yes (4). Scores range from 0-100, with a higher score reflecting a greater disability associated with dizziness. Cut-off scores exist for mild (16-34), moderate (36-52), and severe (54+) disability, with an 18-point change in score considered clinically meaningful (Jacobson & Newman, 1990).

The Neck Disability Index (NDI)

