Eye tracking	Saccades			Х
	King Devick Test			X
Symptoms	Post- Concussion Symptom Scale			X

 Table 2: Outcome measures

(*M*/*L*=medial/lateral; *A*/*P*= anterior/posterior; COP,=centre of pressure)

Interventions

Balance Testing Protocol

All participants will be asked to perform a repeated measure of 2 different balance tasks under 2 different treatment conditions as outlined below. Each trial of balance will take 2 min to administer, and will be performed with the participant wearing socks. Before and after each trial, participants will be asked to rate if they are experiencing any headache, dizziness, nausea, or fogginess on a scale of 0 to 10. Following each trial, a washout period will be given as the greater of a minimum of 1 minute of rest or until symptoms aggravated by the task return to their pretrial baseline. A time period of two minutes was chosen as a sufficient interval over which to collect stable COP data according to the International Society for Posture and Gait Research (Scoppa, Capra, Gallamini, & Shiffer, 2013), while aligning with time required to complete the KDT.

For balance task A, participants will be asked to stand with their feet shoulder width apart on the BTS with their hands placed on their hips. They will be asked to hold this position for two minutes with their eyes open, vision fixed on a small target (dot), and to focus on standing as still as possible.

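### The protocol asks whether BNO reduces symptoms, but its only designated symptom outcome, the PCSS, is timed before either condition, and the per-trial 0-10 ratings that could show the contrast have no outcome role

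*Protocol*

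**What the plan says.** Three parts of the protocol pose or claim a treatment effect on symptoms.

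- **Abstract, Introduction:** "It is hypothesized that BNO will improve balance and saccadic eye function, and reduce symptoms". The Abstract's Methods paragraph also lists self-reported symptoms and disability as secondary outcomes.
- **Introduction and Objectives:** the evidence gap is described as the effect of BNO on COP velocity, "objective metrics of saccadic eye movement, and symptoms during the performance of single- and visually-based cognitive dual-task balance conditions". The text continues: "This study aims to address this gap by assessing the efficacy of a BNO intervention trial". The overarching question is "What is the effect of BNO compared with no binasal occlusion on measures of static balance, saccadic eye movement functions, and symptoms".
- **Conclusion:** the primary and secondary outcomes are said to inform BNO efficacy across four domains: sway, saccadic function, symptoms and disability.

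The operative sections are narrower.

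- **Objective 5** covers symptoms only as an association: "measure the association between self-reported symptoms, disability, and objective measures of balance in adults".
- **Table 2** has one entry in its symptom domain, the Post-"Concussion Symptom Scale", marked secondary. The Dizziness Handicap Inventory (DHI) and Neck Disability Index (NDI) are marked as baseline disability.
- **Secondary outcomes** gives the timing: "Prior to postural sway data collection, participants will be asked to complete 4 questionnaires, including a participant demographic questionnaire, the post-concussion symptom scale (PCSS", followed by DHI and NDI. No repeat is stated.
- **The PCSS section** says the scale "measures the severity of each symptom experienced that day".
- **Balance Testing Protocol** asks for a 0-10 rating covering headache, dizziness, nausea and fogginess before and after each trial. The ratings are not in Table 2 or under Secondary outcomes.
- **Planned statistical analyses** compares conditions on the COP variables, KDT time and saccade count. PCSS, DHI and NDI enter only Spearman correlations.

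**The concern.** A secondary outcome should be able to answer the question attached to it. Here the question is whether symptoms differ between BNO and unoccluded vision in the same person. The measure named for symptoms is completed before the participant has met either condition, and its recall period is the whole day, not a single trial.

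The stated hypothesis that BNO reduces symptoms, and the symptom part of the overarching question, therefore have no designated outcome that can support or refute them. Suitable data are requested at every trial but left without outcome status. If that status is settled only after the data are seen, the symptom result is open to selective reporting. This matters more because participants can tell occluded from unobstructed lenses.

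**Working it through.** The point rests on what is measured when. The plan gives no figure to reproduce, so the check sets the passages side by side and counts the contrasts available.

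**Inputs:** 40 participants (Sample size); 2 tasks and 2 conditions (Design); PCSS, DHI and NDI once, before sway collection (Secondary outcomes); symptom ratings before and after each trial (Balance Testing Protocol).

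| Measure | Status in Table 2 | Stated timing | Within-person BNO-control difference? |
|---|---|---|---|
| COP variables | Primary | Each trial, both conditions | Yes |
| Saccades, KDT | Secondary | During trials, both conditions | Yes |
| PCSS | Secondary | Before any sway data | No |
| DHI, NDI | Baseline disability | Before any sway data | No |
| 0-10 symptom ratings | Not listed | Before and after each trial, both conditions | Yes |

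**PCSS.** Each participant has one score, belonging to neither condition. The number of participants with a BNO-minus-control PCSS difference is 0 of 40, whatever test is applied.

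**0-10 ratings.**
- Trials: 2 tasks × 2 conditions = 4 per participant.
- Rating occasions: 4 trials × 2 (before, after) = 8, of which 4 follow a trial.
- Task-specific BNO-control comparisons: 2 tasks × 1 combined score = 2, or 2 tasks × 4 symptoms = 8. The text allows either reading.

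The ratings also match the gap sentence in the Introduction, which concerns symptoms while the balance tasks are being performed.

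**Domains in the Conclusion.** Of the four efficacy domains, two (sway and saccadic function) have a designated outcome measured under both conditions. Symptoms and disability do not.

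**What is consistent.** The five objectives, the detailed hypotheses that follow them and the planned between-condition tests all confine BNO contrasts to sway, KDT time and saccades. PCSS before testing is suitable timing for objective 5. The sample size rests on COP excursion and does not depend on the symptom outcome.

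**The case against.** The strongest reply is that the operative text is coherent. Objectives, detailed hypotheses and analyses treat symptoms only by association, so the mismatch is loose wording in the Abstract, the overarching question, the gap sentence and the Conclusion. This stands in large part. It limits the point to a mismatch between outcome and stated question, and it is why removing the wording is an acceptable remedy. It does not remove the mismatch, because a formal hypothesis and the overarching question still pose an effect that the designated outcome cannot show.

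A second reply is that the Abstract's generic mention of self-reported symptoms could include the 0-10 ratings, and that a statistical analysis plan could analyse them. A plan could do so, and the lack of a specified test for the ratings is not counted here as a fault. But Table 2 resolves the symptom domain to PCSS alone, and the only use the protocol gives for symptom state around trials is the length of the rest period.

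Two stronger readings are tempting, and neither is supported:

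- **That the trial cannot answer the symptom question at all.** That is true of PCSS at its stated timing, but not of the ratings.
- **That the publication list in Ethics and Dissemination flatly contradicts the Conclusion.** The list names sway and saccades as efficacy topics and puts symptoms and disability under association. It is introduced as a list of what publications include, so it does not strictly exclude other efficacy topics.

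**Conclusion.** The point holds as a mismatch between the designated outcome and the stated question. As written, the only symptom outcome in Table 2 gives no BNO-control difference for any of the 40 participants and serves only the association objective. The ratings that could give one, requested on 8 occasions per participant, are not designated. Disability in the Conclusion's efficacy sentence has the same problem, since DHI and NDI are also taken only before testing.

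A reader might infer that the main result is compromised. It is not: the primary COP analysis and the sample size are unaffected. The change should be made, but it concerns a secondary question.

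The conclusion assumes that PCSS is given once. This is inferred from the only timing stated. Figure 1, which summarises the design, is not shown, and a repeat of PCSS under each condition would change the conclusion.

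**What to change.** **Preferred: designate the ratings.**

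1. In Table 2 and under the Secondary outcomes heading, mark PCSS as a baseline measure alongside DHI and NDI. Keep all three for the correlation objective.
2. Add the per-trial 0-10 rating as the secondary symptom outcome, and state whether it is one combined score or four.
3. Compare BNO with control within participant for each task, using either the post-trial rating or the pre-to-post change, chosen in advance. A Wilcoxon signed-rank test would serve.
4. Edit the Abstract's secondary-outcome sentence to match: symptoms by the per-trial rating, disability as a baseline measure only. Otherwise the Abstract would conflict with the revised table.

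No new procedure or visit time is needed, since the ratings are already requested; the data form must record them. The costs are 2 added comparisons with one combined score, or 8 with four symptoms; a scale not shown to be validated; and self-report by participants who are not blinded. For these reasons the outcome should stay secondary.

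**Alternative: withdraw the claim.** Remove the symptom-effect wording from the Abstract hypothesis, the gap sentence, the overarching question and the Conclusion's efficacy sentence. Revise the Abstract's secondary-outcome sentence so that symptoms and disability are described as baseline or association measures. This is wording only, but it gives up the symptom question.

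**In either case,** drop disability from the Conclusion's efficacy sentence.
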